16.2 Appendix 2: Borg CR 10 scale and test instructions

Use this rating scale to report how strong your perception of exertion is. First look at the verbal expressions. Start with them and then the numbers. Of these ten (10) or “Extremely strong – Maximal” is a very important intensity level. This is the most intense perception or feeling you have ever had.

If your experience or feeling is “Very weak”, you should say “1”, if it is “Moderate”, say “3”. Note that “Moderate” is “3” and thus weaker than “Medium”, “Mean” or “Middle”. If the experience is “Strong” or “Heavy” (it feels “Difficult”) say “5”. Note that “Strong” is about half of “Maximal”. Is your feeling “Very strong”, choose a number from 6 to 8. If your perception or feeling is stronger than “10”, “Extremely strong – Maximal” you can use a larger number, e.g. 12 (that’s why “Absolute maximum” is marked with a dot “•”). It is very important that you report what you actually experience or feel, not what you think you should report. Be as spontaneous and honest as possible and try to avoid under- or overestimating. Look at the verbal descriptors and then choose a number.

When rating your exertion give a number (in principle any kind of decimal number is allowed) that corresponds to how hard and strenuous you perceive the work to be. The perception of exertion is mainly felt as strain and fatigue in your muscles and as breathlessness or any aches.

Clinical Study Protocol
No. BAY 1021189 / 19334

22 FEB 2018

Version no. 1.0

Page: 81 of 81

0 “Nothing at all”, means that you don’t feel any exertion whatsoever, no muscle fatigue, no breathlessness or difficulties breathing.

0.3

0.5 “Extremely weak”, “Just noticeable”

0.7

1 “Very weak” means a very light exertion. As taking a shorter walk at your own pace.

1.5

2 “Weak”, “Light”

2.5

3 “Moderate” is somewhat but not especially hard. It feels good and not difficult to go on

4

5 “Strong – Heavy”. The work is hard and tiring, but continuing isn’t terribly difficult. The effort and exertion is about half as intense as “Maximal”.

6

7 “Very strong” is quite strenuous. You can still go on, but you really have to push yourself and you are very tired.

8

9

10 “Extremely strong – Maximal” is an extremely strenuous level. For most people this is the most strenuous exertion they have ever experienced previously in their lives.

11

=

- Is “Absolute maximum – Highest possible” for example “12” or even more.

## Abbreviations

ACE	Angiotensin converting enzyme
ACIR	Assessment Criteria Identification Requirement
AE	Adverse event
ALT	Alanine aminotransferase
AN(C)OVA	Analysis of (Co-)Variance
ARB	Angiotensin receptor blocker
ATC	Anatomical Therapeutic Chemical
BMI	Body mass index
CAD	Coronary artery disease
CDF	Cumulative distribution function
cGMP	Cyclic guanosine monophosphate
CKD	Chronic kidney disease
COPD	Chronic obstructive pulmonary disease
CSR	Clinical Study Report
CSS	Clinical Summary Score
CV	Cardiovascular
DSMC	Data Safety Monitoring Committee
DBP	Diastolic blood pressure
ECG	Electrocardiogram
eCRF	Electronic Case Report Form
EF	Ejection fraction
eGFR	Estimated glomerular filtration rate
e.g.	exempli gratia , for example
FAS	Full analysis set
GCP	Good Clinical Practice
HEOR	Health Economics, Outcomes & Reimbursement
HF	Heart failure
HFrEF	Heart failure with reduced ejection fraction
HFpEF	Heart failure with preserved ejection fraction
HR	Heart rate
ICH	International Committee on Harmonization
i.e.	id est , that is
IV	Intravenous
KCCQ	Kansas City Cardiomyopathy Questionnaire
LAV	Left atrial volume
LLOQ	Lower limit of quantification
LVEF	Left ventricular ejection fraction
MACE	Major adverse cardiovascular event
MAP	Mean arterial pressure
MAR	Missing at random
MedDRA	Medical Dictionary for Regulatory Activities
MMRM	Mixed-effects model for repeated measures
MNAR	Missing not at random
MRA	Mineralocorticoid receptor antagonist
NO	Nitric oxide
NT-proBNP	N-terminal pro-brain natriuretic peptide
NYHA	New York Heart Association
o.d.	omni die , once daily
OSS	Overall Summary Score
PD	Pharmacodynamics

# Statistical Analysis Plan

---

Protocol No.: **BAY 1021189 /19334**

Page: 5 of 40

PDF	Probability Density Function
PLS	Physical Limitation Score
PK	Pharmacokinetics
PKS	Pharmacokinetic analysis set
PP	Pulse pressure
PPS	Per protocol set
PT	Preferred term
QoL	Quality of Life
ROC	Receiver operating characteristics
SAC	Statistical Analysis Center
SAE	Serious adverse event
SAF	Safety analysis set
SAP	Statistical Analysis Plan
SBP	Systolic blood pressure
SFS	Symptom Frequency Score
sGC	Soluble guanylate cyclase
SMQ	Standard MedDRA query
SOC	System organ class
TEAE	Treatment emergent adverse event
TLF	Tables, listings, and figures
TSS	Total Symptom Score
ULN	Upper limit of normal
VAS	Visual analogue scale
WCHF	Worsening chronic heart failure
WHO-DD	World Health Organization Drug Dictionary

## 1. Introduction

Patients hospitalized with heart failure (HF) with preserved ejection fraction (HFpEF) are a large and growing population. The relative proportion of HFpEF has increased to more than 50% of all HF hospitalizations [1]. Event rates after hospitalization in patients with HFpEF are as high as in patients with HF with reduced ejection fraction (HFrEF). Since patients with HFpEF are highly symptomatic with a poor quality of life, it is important to find new therapies that can alleviate symptoms and improve patient well-being [2].

No specific therapy has been currently established for HFpEF patients, and recommendations are limited to symptomatic treatment of congestive symptoms by diuretics, and to treating causes and comorbidities including hypertension, coronary artery disease, and atrial fibrillation [3]. Trials that established the clinical benefits of angiotensin converting enzyme (ACE) inhibitors, angiotensin receptor antagonists, and  $\beta$ -blockers have all selected patients on the basis of reduced EF. Subsequent trials in patients with HFpEF did not confirm equal effectiveness in this subgroup [4]. Therefore, there is need for new drug targets such as cyclic guanosine monophosphate (cGMP).

Vericiguat has been evaluated in approximately 65 preclinical studies and has been administered to over 500 healthy patients in 19 completed Phase I studies with single- and multiple-dose administration, and in approximately 740 heart failure patients in two Phase IIb studies (SOCRATES- REDUCED and SOCRADES- PRESERVED) that studied vericiguat in worsening chronic heart failure patients with HFrEF and with HFpEF. In the ongoing phase III event-driven outcome trial VICTORIA (NCT02861534), as of Aug 31 2018, 3791 patients with HFrEF out of a planned total sample size of 4872 have been randomized to vericiguat 10 mg target dose or placebo with a median study drug treatment duration at that time of 5 months. The study treatment duration is planned to continue until 2020 for a median follow-up duration of 18 months.

In SOCRADES-PRESERVED 4 different dose regimens of vericiguat were studied in patients with chronic HFpEF enrolled within 1 month after a qualifying heart failure decompensation event [5]. Data from SOCRADES-PRESERVED established 2.5 mg vericiguat as the safe and well tolerated starting dose. Uptitration by two dose doublings with 14 day intervals each to a target dose of 10 mg was tolerated in patients with HFpEF without an increase in adverse events compared to placebo, with low discontinuation rates in all groups, and no changes in blood pressure at 10 mg compared to placebo. Although analyses of the primary efficacy variables in SOCRADES-PRESERVED did not demonstrate changes in NT-proBNP and LAV at 12 weeks in the vericiguat dose groups compared to placebo, patients receiving vericiguat in the 10 mg target dose arm experienced a more pronounced improvement in health related QoL, physical limitations, NYHA class, signs and symptoms of congestion and trends towards improved diastolic function at 12 weeks [5,6].

The Kansas City Cardiomyopathy Questionnaire (KCCQ) has been widely used in HF trials. In SOCRADES-PRESERVED, improvements in the KCCQ overall summary score (OSS) as well as the clinical summary score (CSS) were observed. Consistent changes in other domains of the KCCQ were also noted. However, the improvement appeared to be driven primarily by improvements in the physical limitation score (PLS). KCCQ PLS has previously been

validated against the distance covered in a 6MWT, NYHA class, and physical limitation domains within other quality of life (QoL) instruments including the 36-Item Short Form Survey in patients with HF [7]. Improvements in physical functioning and reduction in symptom frequency are considered to be direct measures of treatment benefit in patients with HFpEF, and have been shown to be associated with subsequent reductions in mortality and hospitalizations [8]. These data generate the hypothesis that vericiguat improves physical functioning and clinically relevant patient-reported outcomes in patients with HFpEF. Based on these data, the VITALITY phase 2 trial (study 19334) has been designed to study whether in patients with HFpEF vericiguat 10 mg or 15 mg improves the KCCQ PLS compared to placebo after 24 weeks of treatment.

This statistical analysis plan (SAP) is based on the study protocol (Version 1.0 dated 22 FEB 2018) and describes the interim and final analyses of study 19334.

## **2. Study Objectives**

The primary hypothesis is treatment with vericiguat 10 mg or 15 mg in patients with HFpEF improves physical functioning measured by the KCCQ PLS compared to placebo after 24 weeks of treatment. The secondary hypothesis is treatment with vericiguat 10 mg or 15 mg in patients with HFpEF improves walking distance as measured by the 6MWT compared to placebo after 24 weeks of treatment. The study is designed to have enough power for the primary and secondary hypotheses testing. Other objectives are listed only for descriptive purposes.

Primary objectives:

- To evaluate the efficacy of vericiguat 10 mg in comparison to placebo on improving physical functioning as measured by KCCQ PLS from baseline to week 24.
- To evaluate the efficacy of vericiguat 15 mg in comparison to placebo on improving physical functioning as measured by KCCQ PLS from baseline to week 24.
- To evaluate the safety and tolerability of vericiguat.

Secondary objectives:

- To evaluate the efficacy of vericiguat 10 mg in comparison to placebo on improving distance traveled on a 6MWT from baseline to week 24.
- To evaluate the efficacy of vericiguat 15 mg in comparison to placebo on improving distance traveled on a 6MWT from baseline to week 24.
- To evaluate the efficacy of vericiguat 10 mg in comparison to placebo in increasing the proportion of patients with KCCQ PLS improvement from baseline by >5 points at 24 weeks and other thresholds (e.g. >3, >7, >10, >15, >20), and the proportions with these improvements in the other KCCQ domains OSS, CSS, TSS and SFS.

- To evaluate the efficacy of vericiguat 15 mg in comparison to placebo in increasing the proportion of patients with KCCQ PLS improvement from baseline by >5 points at 24 weeks and other thresholds (e.g. >3, >7, >10, >15, >20), and the proportions with these improvements in the other KCCQ domains OSS, CSS, TSS and SFS.
- To evaluate the efficacy of vericiguat 10 mg in comparison to placebo in decreasing the proportion of patients with KCCQ PLS decline from baseline by >5 points at 24 weeks and the proportions with decline in the other KCCQ domains OSS, CSS, TSS and SFS.
- To evaluate the efficacy of vericiguat 15 mg in comparison to placebo in decreasing the proportion of patients with KCCQ PLS decline from baseline by >5 points at 24 weeks and the proportions with decline in the other KCCQ domains OSS, CSS, TSS and SFS.

## Other objectives:

- To evaluate the efficacy of vericiguat 10 mg and the efficacy of vericiguat 15 mg in comparison to placebo on improving:
  - Symptom frequency as measured by the KCCQ SFS
  - Perceived exertion experienced by patients during 6MWT as measured by Borg CR 10.
  - Other patient-reported outcomes such as the generic health-related quality of life measure EQ-5D-5L and the Fried-based frailty score
  - NYHA class
  - Laboratory variables such as NT-proBNP from baseline to 24 weeks
- To collect and summarize death including cardiovascular death and CV hospitalizations including heart failure hospitalizations, MI and stroke, and outpatient HF events.
- To create the cumulative distribution function of KCCQ PLS, OSS, CSS, TSS and SFS change from baseline to 24 weeks.
- To evaluate PK of vericiguat in patients with HFpEF, and
- To evaluate the concentration-QTc relationship of vericiguat at the 15 mg dose level.
- Optional pharmacogenetic research: To explore the relationship between genetic variation and clinical characteristics of patients, independent and dependent of the treatment administered. Variations across the human genome may be analyzed for association with clinical data collected in this study.
- To evaluate further biomarkers to investigate the drug (i.e. mode-of-action-related effect and / or safety) and / or the mechanisms of the disease

- Optional accelerometry substudy: to collect exploratory data by activity tracking

**Note:** Analyses for PK, biomarker, and optional objectives (including accelerometry) will be specified in a separate supplementary SAP.

[figure not shown]
### 3. Study Design

This is a randomized, parallel-group, placebo-controlled, double-blind, multi-center trial of vericiguat in patients with HFpEF to be conducted in conformance with GCP. Approximately 735 patients will be randomized as described in [Figure 3-1](#) to evaluate the efficacy of vericiguat 10 mg and 15 mg in comparison to placebo on improving physical functioning from baseline to week 24. To reduce heterogeneity in the studied population patients younger than 45 years of age are not eligible. Patients are expected to be on a background treatment for concurrent conditions including hypertension (anti-hypertensives) and volume overload (diuretics).

Screening may be initiated any time after admission of a patient to the hospital for HF, before or after discharge, and up to 6 months after hospitalization for HF. Use of IV diuretic treatment for HF, even without hospitalization, is indicative of HF decompensation and accepted as a qualifying HF event equivalent to hospitalization. The most recent decompensation should be considered for qualifying the patient for the study. In either scenario, HF must be the primary reason for hospitalization or IV diuretic treatment. Patients will be randomized within up to 4 weeks after the screening visit and within up to 6 months after the onset of the qualifying event of hospitalization for HF or treatment with IV diuretic for HF (see [Figure 3-1](#)).

Primary endpoint assessment is at week 24. All patients will be followed until study completion to assess for vital status and all study endpoints until week 28.

**Figure 3-1 Study design**

EF, ejection fraction; FU, follow-up; HF, heart failure; KCCQ, Kansas City Cardiomyopathy Questionnaire; LAE, left atrial enlargement; LVH, left ventricular hypertrophy; NT-proBNP, N-terminal pro-brain natriuretic peptide; NYHA, New York Heart Association; PLS, physical limitation score; V, Visit. KCCQ as the entire questionnaire is administered, not just the PLS domain.

## Stratification

Patients will be randomized within 4 weeks of the screening visit and within up to 6 months after the date of hospitalization for HF or treatment with IV diuretic for HF, and randomization will be stratified according to region and heart rhythm at baseline ECG.

### Region

- Americas
- Europe (incl. Israel and South Africa)
- Asia/Pacific

### Heart rhythm

- Atrial fibrillation (defined as atrial fibrillation or atrial flutter in baseline ECG)
- Sinus rhythm (defined as no atrial fibrillation and no atrial flutter in baseline ECG)

## Treatment

Patients will be randomized 1:1:1 within 4 weeks after the Screening Visit to either:

1. Placebo arm: placebo and sham up-titration at weeks 2, 4, and 6
2. 10 mg arm: vericiguat, which will be started at 2.5 mg at randomization and up-titrated to 5 mg at week 2, and to 10 mg at week 4, with sham titration at week 6.
3. 15 mg arm: vericiguat, which will be started at 2.5 mg at randomization and up-titrated to 5 mg at week 2, to 10 mg at week 4, and to 15 mg at week 6.

## Withdrawal from study

Unnecessary withdrawal of patients from the study follow-up should be avoided and all efforts should be taken to motivate patients to adhere to all study procedures and to be followed until the end of the trial. All patients will be followed until study completion to assess for vital status and all study endpoints until week 28.

The investigator should explore all possible options to reach a patient who fails to return to a visit or to respond to the site contact attempts. The site must document all attempts to try to contact the patient in the medical records / source documents. In order to avoid loss-to-follow-up, the investigator should ask the patient at the study start for the contact details of a relative or friend who can be contacted in case the patient cannot be reached. Patients should not be withdrawn from follow-up unless the patient explicitly withdraws consent to be contacted. All

efforts should therefore be made to discuss solutions with the patient that would enable the patient to continue with follow-up in order to minimize the number of patients who withdraw such consent. The vital status will be collected for all randomized patients who have not specifically withdrawn consent for further study follow-up by any method (telephone call, email etc.), irrespective of completion of study procedures.

### **End of study**

The end of the study as a whole will be reached as soon as the last visit of the last patient has been reached in all centers in all participating countries (EU and non-EU).

## **4. General Statistical Considerations**

### **4.1 General Principles**

The statistical analyses will be performed using the software package SAS release 9.2 or higher (SAS Institute Inc., Cary, NC, USA) [9].

All variables will be analyzed by descriptive statistical methods. For continuous data, the summary statistics including mean, standard deviation, minimum, median, quartiles, and maximum, and the number of missing data will be provided. For categorical data, frequency count and percentages will be generated.

All patients will be analyzed according to the assigned treatment group if not specified otherwise. Each treatment group will comprise all patients within one randomized titration scheme regardless of the individual subject's actual titration, i.e. in case a subject could not be up titrated or was down-titrated during the study.

### **On treatment**

A measurement is considered to be "on-treatment," if it was taken during treatment or up to 5 days after end of treatment with study medication.

### **Analysis time point and visit window**

Based on the randomization date, each scheduled visit date will be computed and a midpoint between two adjacent scheduled visit dates will be identified as the boundary of two visit windows. For example, Day 28 will be used to label the boundary between week 2 and week 6 windows. [Table 4-1](#) shows an example of the visit window for each analysis time point for KCCQ. Each visit date will be mapped to one visit window. For any particular window, if there are multiple measurements within the window then the one that is closest to the scheduled visit date will be used. In case there are multiple measurements on the same day, the latest one will be selected. Also note that the baseline is defined as the last non-missing measurement before first intake of study treatment ([Section 4.4.2](#)). In case KCCQ assessments may simultaneously be considered as baseline and follow up, for example if a patient takes first study treatment 14 days after randomization, under such scenario these measurements will be assigned as baseline only.

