- If restart after visit 5 (week 6) restart as soon as possible (with an unscheduled visit if required) and up-titrate according to [Table 7-4](#). Patient will then resume the planned visit schedule. Unscheduled clinic and/or phone contacts can be conducted at the discretion of the investigator. The titration steps must be at least 11 days apart, and if the period between resumption and the next scheduled visit is more than 17 (14+3) days, the patient can attend an unscheduled visit.

Table 7-4: Resumption of study drug intake

Dose step at time of interruption	(mg) at time of interruption	Length of interruption	Restart dose	1 st titration (14±3 days after resumption)	2 nd titration (28±3 days after resumption)	3 rd titration (42±3 days after resumption)
1	Plc or 2.5	Any	Plc or 2.5	Plc or 5	Plc or 10	Plc or 10 or 15
2	Plc or 5	Any	Plc or 2.5	Plc or 5	Plc or 10	Plc or 10 or 15
3	Plc or 10	>5 days	Plc or 2.5	Plc or 5	Plc or 10	Plc or 10 or 15
		≤5 days	Plc or 5	Plc or 10	Plc or 10 or 15	NA ^a
4	Plc or 10 or 15	>5 days	Plc or 2.5	Plc or 5	Plc or 10	Plc or 10 or 15
		≤5 days	Plc or 5	Plc or 10	Plc or 10 or 15	NA ^a

a highest dose achieved in the second titration

NA, not applicable; Plc, placebo

For follow-up of patients after discontinuation see Section 9.1

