9.2.9 Visit 9 End of treatment – Day 168±7 (week 24)

Patients need to come to site without taking the morning dose of the study drug (this applies only for the study drug. All other medications shall be taken as scheduled).

The end of treatment visit should be scheduled at Day 168±7 also in case of premature discontinuation of study drug. All other visits and procedures should continue also if the study drug has been permanently discontinued.

- KCCQ, EQ-5D-5L, PGIC/S (see Section [9.4](#))
- Frailty assessment based on the Fried score
- Assessment of NYHA class
- Concomitant medications (see Section [8.1](#))
- Adverse events (see Section [9.6.1](#))
- Only for patients participating in the optional accelerometry substudy: Activity tracking devices are planned to be collected (see accelerometry manual).
- Physical examination
- Vital signs in sitting position (BP and pulse rate). See Section [9.7.5](#).
- 6MWT
- 12-lead ECG in patients not eligible for PK/QT assessment, see Section [9.7.4](#)
- Only in patients eligible for PK/QT assessment (all patients assessed as eligible based on the baseline ECG, see Section [9.7.4](#)) – ECG and PK sample should be collected time-matched, first ECG, subsequently PK sample:
 - 12-lead ECG (to be performed just before the PK sample is taken) to be taken prior to study drug intake (exact collection time must be documented)
 - Blood sample for PK prior to study drug intake (exact collection time to be documented)
- Central lab blood samples for NT-proBNP, hematology, clinical chemistry, coagulation and biomarkers [9.7.1](#) and blood sample for PK prior to study drug intake (exact collection time to be documented) in all patients, see Section [9.7.4](#)

- Drug accountability, incl. exact time of last dose intake the day before, and collect unused study drug
- Patient to take study drug (exact time of intake must be documented)
- Only in patients eligible for PK/QT assessment (all patients assessed as eligible based on the baseline ECG, see Section 9.7.4) – ECG and PK sample should be collected time-matched, first ECG, subsequently PK sample:
 - 12-lead ECG (to be performed just before the PK sample is taken) to be taken 1-2 h after study drug intake, exact collection times must be documented)
 - Blood sample for PK 1-2 h after study drug intake, exact collection time must be documented)

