9.2.11 Premature discontinuation visit – at time of permanent discontinuation

This visit is applicable only for patients who prematurely discontinue the study drug intake (Either by decision of the investigator or by the patient.)

- KCCQ, EQ-5D-5L, PGIC/S (see Section 9.4)
- Frailty assessment based on the Fried score
- Assessment of NYHA class
- Concomitant medications (see Section 8.1)

- Adverse events (see Section 9.6.1)
- Physical examination incl. weight
- Vital signs (BP and pulse rate). See Section 9.7.5.
- 12-lead ECG (see Section 9.7.4)
- 6MWT
- Central lab blood sample for NT-proBNP, hematology, clinical chemistry, coagulation and biomarkers.
- Drug accountability, incl. exact time of last dose intake the day before, and collect unused study drug
- Schedule Visit 12 for 30±7 days after last dose

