### **6.3.3 Further safety parameters**

#### **6.3.3.1 Laboratory parameters**

Summary statistics including changes from baseline will be calculated by treatment group and visit for all quantitative laboratory parameters. The summary statistics for troponin T and eGFR will also be provided by treatment group.

The number of patients with transitions from baseline with respect to reference range categories (low, normal, high) will be provided by treatment group and visit. In addition, the number of patients with treatment-emergent abnormal laboratory values above or below the normal range will be tabulated by treatment group and overall.

To assess acute renal failure, the number and incidence of patients with increase in serum creatinine  $>0.3$  mg/dL,  $>0.5$  mg/dL, and  $\geq \times 2$  from baseline, as well as the number and incidence of patients with decrease in eGFR  $>50\%$  or to  $<15$  mL/min/1.73m^2 will be presented by visit and treatment group.

The number and incidence of patients with ALT  $> 3 \times$  upper limit of normal (ULN), and total bilirubin  $> 2 \times$ ULN will be presented by visit and treatment group.

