#### **6.3.3.2 Vital signs**

The absolute values and the changes from baseline values at each visit will be summarized by treatment group using descriptive statistics for systolic blood pressure (SBP), diastolic blood pressure (DBP), heart rate (HR).

The change in vital signs parameters from baseline to week 24 will be analyzed by two-sided two-sample t-tests comparing each individual vericiguat treatment group with the placebo treatment group at the 5% level in an explorative setting.

The number of patients with systolic blood pressure below 90 mmHg, based on the individual measurements rather than the mean value, will be displayed by visit and by treatment group. A frequency listing of all patients with systolic blood pressure below 90 mmHg post baseline will be provided.

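### The visit-window rule usually drops the discontinuation lab from the by-visit creatinine, eGFR, ALT and bilirubin threshold counts, and no any-time count recovers it

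*SAP*

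**What the plan says.** The window rule stands in SAP 4.1 (General Principles). Boundaries come from the visit schedule: "a midpoint between two adjacent scheduled visit dates will be identified as the boundary of two visit windows". Every visit date goes into one window, and "if there are multiple measurements within the window then the one that is closest to the scheduled visit date will be used". SAP Table 4-1 is introduced as illustration, since it "shows an example of the visit window for each analysis time point for KCCQ". Nothing limits the rule to efficacy variables. The same section defines on-treatment as during treatment or up to 5 days after its end.

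SAP 6.3.3.1 sets out the renal counts ("To assess acute renal failure, the number and incidence of patients with increase in serum creatinine" above stated cut-offs, with eGFR falls) and the hepatic counts (ALT above 3 times and bilirubin above 2 times the upper limit of normal). All are by visit and treatment group. None refers to the on-treatment definition, and no any-time or worst-value count is planned.

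The Protocol schedules post-baseline central labs at Visit 6 (9.2.6) and Visit 9 (9.2.9). The premature discontinuation visit, Visit 11, adds another (9.2.11): "Central lab blood sample for NT-proBNP, hematology, clinical chemistry, coagulation and biomarkers". Stopping drug does not end the schedule (9.2.9): "All other visits and procedures should continue also if the study drug has been permanently discontinued".

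**The concern.** A lab taken when a patient comes off drug is among the values most likely to show renal or hepatic harm. Under the plan it shares a window with the week 8 or week 24 lab and competes with it on distance from the scheduled day, not on severity or on whether the patient was taking drug. If the scheduled lab wins, the threshold count for that patient may rest on a value taken after the drug was stopped, when an abnormality may have resolved.

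Safety and tolerability is a primary objective, and Protocol 3.3 says that there are no data with 15 mg in heart failure patients. If stopping differs between arms, the loss from these counts would differ too. The documents give no stopping rates for this trial, so that difference cannot be sized.

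**Working it through.** **Inputs.** Midpoint and closest-date rules, and the 5-day on-treatment definition: SAP 4.1. KCCQ target days 14, 42, 84, 126, 168, 196: SAP Table 4-1. Central labs at Day 56 and Day 168: Protocol 9.2.6 and 9.2.9. Discontinuation lab: Protocol 9.2.11. No central lab is listed at either follow-up visit (9.2.10, 9.2.12). Assumption: the discontinuation lab is drawn on the stop day.

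**1. Reproduce the plan's own windows.** Boundary = (earlier day + later day)/2:
- (14+42)/2 = 28
- (42+84)/2 = 63
- (84+126)/2 = 105
- (126+168)/2 = 147
- (168+196)/2 = 182

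Each equals a window start in Table 4-1, so the boundary day opens the later window. Day 28 is the date of Visit 4, where Protocol 9.2.4 lists no KCCQ. The example therefore builds windows on the variable's own schedule.

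**2. Apply the same rule to central labs.** (56+168)/2 = 112. Windows: Day 2 to 111 (week 8) and Day 112 onward (week 24).

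**3. Classify each possible stop day, 2 to 167 (166 days),** with scheduled labs attended on the nominal day.

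| Stop day | Days | Value kept | More than 5 days after stop |
|---|---|---|---|
| 2–55 | 54 | Day 56, post-stop | 49 (stop on or before Day 50) |
| 56 | 1 | same day | – |
| 57–111 | 55 | Day 56, earlier and on drug | – |
| 112–167 | 56 | Day 168, post-stop | 51 (stop on or before Day 162) |

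- Displaced: 54 + 55 + 56 = 165 of 166.
- Replaced by a post-stop value: 54 + 56 = 110 (66%).
- Of these, more than 5 days after the stop, so outside the SAP's on-treatment definition: 49 + 51 = 100 (60% of 166).
- Replaced by the earlier on-drug value: 55 (33%).

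**4. Allow for visit tolerances** (Day 56±3, Day 168±7). The discontinuation lab can be strictly closer only for stops on Days 54–58 (5 days) or 162–167 (6 days): at most 11/166 = 6.6%. The SAP gives no rule for ties between different days. Awarding every tie to the discontinuation lab gives 7 + 7 = 14, or 14/166 = 8.4%.

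**5. Allow for missed visits.** Let *a* be attendance at the next lab visit, with stop days uniform and the week 8 lab drawn for stops on Days 57–111. Kept = [1 + 110(1 − *a*)]/166; replaced by a post-stop value = 110*a*/166.
- *a* = 0.8: kept 23/166 = 14%; post-stop 88/166 = 53%.
- *a* = 0.5: kept 56/166 = 34%; post-stop 55/166 = 33%.

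The on-drug replacement stays at 33%.

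**6. Other reading: every visit date sets a boundary.** The lab windows become Day 49–69 and Day 147–181.
- Replaced by a post-stop value: Days 49–55 and 147–167, 7 + 21 = 28 (17%).
- Replaced by the earlier on-drug value: Days 57–69, 13 (8%).
- Same day: 1.
- Left in a window of their own: 166 − 28 − 13 − 1 = 124 (75%).

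**The case against.** **Other outputs give cover.** SAP 6.3.3.1 also tabulates treatment-emergent out-of-range results by group and overall, not by visit. Protocol 9.6.1.1 counts abnormal laboratory findings as adverse events, and SAP 6.3.1 tabulates by arm the events that cause discontinuation. SAP 5.1 puts all patients' data in listings, and Protocol 9.6 classes laboratory data as exploratory safety variables. This stands as partial cover. The out-of-range table uses reference limits, not the renal and hepatic cut-offs, and the SAP does not say whether window selection applies to it. Adverse event tables depend on what was reported, and listings are not counts by arm.

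**The lab windows are inferred.** The SAP prints windows only for KCCQ. That is true, and step 6 shows that the other reading saves most discontinuation labs. The KCCQ example points the other way, and the SAP does not settle it for labs.

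**By-visit counts answer a by-visit question.** They do, which is a reason to keep them and add a count beside them.

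**Blood pressure.** A reader might infer that low pressures at unscheduled visits vanish in the same way. The documents do not establish this. SAP 6.3.3.2 counts "The number of patients with systolic blood pressure below 90 mmHg, based on the individual measurements rather than the mean value". That may mean every reading, or the three readings within a visit. It also lists every patient with a post-baseline value below 90 mmHg. Hypotension events have their own tables by arm (SAP 6.3.2). The Protocol's provision that "Unscheduled clinic and/or phone contacts can be conducted at the discretion of the investigator" concerns restarting after an interruption and does not say that pressure is recorded. Nothing shows that a low reading would be replaced by an off-drug one. If Visit 5 on Day 42 displaced a low reading on Day 47 while treatment continued, the kept value would itself be on drug.

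**Conclusion.** The point holds for the laboratory thresholds. With windows on the lab schedule and the scheduled lab attended, the discontinuation lab usually drops out of the by-visit creatinine, eGFR, ALT and bilirubin counts. On nominal dates the value that stands in is post-stop for 110 of 166 stop days and on drug for 55.

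The size rests on three assumptions: windows follow the lab schedule, the discontinuation lab falls on the stop day, and the scheduled labs are attended. A reader might turn step 4 into a claim that over 90% of patients who stop lose their discontinuation lab. The documents do not support that: the figure is a share of calendar days, and neither stop timing nor attendance is given. Nor is the replacement always off drug. For SBP below 90 mmHg only a clarification is needed. No confirmatory efficacy result is affected.

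**What to change.** In SAP 6.3.3.1, keep the by-visit tables. For each creatinine, eGFR, ALT and bilirubin threshold, add a patient-level count per arm of any occurrence on treatment, with its denominator. Base it on the worst on-treatment value (highest creatinine, ALT and bilirubin; lowest eGFR) from all central lab results, including Visit 11 and unscheduled samples, under the SAP's existing 5-day definition. In SAP 4.1, state that closest-to-schedule selection does not apply to these counts.

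In SAP 6.3.3.2, add the same any-time count by arm for SBP below 90 mmHg beside the by-visit table and the listing, and say that it uses all individual readings.

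Cost: SAP wording and one extra derived record, with no new data. The any-time counts will not match the by-visit summaries, which use a single record per window; a table footnote should say so.
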